4.6.2 Procedure if the Study is Put on Hold

If the Investigator detects 1 of the holding rules, he/she will immediately put the enrollment or the vaccination on hold and he/she will immediately inform the Sponsor and enter the data in the electronic case report form (eCRF), but all other procedures relating to safety and immunology will continue. In case 1 of the holding rules (1a, 1b, or 1c) is met, the iSRC will meet urgently and review the unblinded data. During this time the study will be kept on hold. The iSRC will inform the study Clinical Research and Development Lead (CRDL) who will inform the relevant bodies of the Sponsor about the outcome of the review and the recommendation on whether to suspend, modify, or continue the conduct of the study on all groups or on selected groups. The decision regarding the further conduct of the study will be documented and provided in writing to the Investigators.

During this review period, the study will be temporarily stopped, while the decision is being made. In case of a decision to stop the study, a letter indicating the reason will be sent to the Institutional Review Board (IRB)/Independent Ethics Committee (IEC) by the Investigator and to the Regulatory Agency by the Sponsor.

5.0 STUDY POPULATION

5.1 Inclusion Criteria

Deviations from inclusion criteria are not allowed because they can potentially jeopardize the scientific integrity, regulatory acceptability of the study, or subject safety. Therefore, adherence to the criteria as specified in the protocol is essential.

All subjects must satisfy ALL the following criteria at study entry:

1. Subjects who, in the opinion of the Investigator, can and will comply with the requirements of the protocol (eg, completion of the diary cards, return for Follow-up Visits).
2. Written or witnessed/thumb print informed consent obtained from the subject prior to performance of any study specific procedure.
3. **For Step 1 only:** A male or female between, and including, 18-45 years of age at the time of the first vaccination.
4. **For Steps 2, 3, and 4:** A male or female between, and including, 50-70 years of age at the time of the first vaccination.
5. Healthy subjects (ie, without progressive, unstable, or uncontrolled clinical conditions) as established by medical history (as verified by either a personal physician or medical practitioner, as appropriate) and clinical examination before entering into the study.
6. Subjects free of any uncontrolled chronic illnesses as established by medical history and clinical examination before entering into the study.
7. Female subjects of nonchildbearing potential may be enrolled in the study.
 - Nonchildbearing potential is defined as premenarche, current bilateral tubal ligation or occlusion, hysterectomy, bilateral ovariectomy, or postmenopause (refer to [Appendix 7](#) for definitions of premenarche and postmenopause).

Female subjects of childbearing potential may be enrolled in the study, if the subject (refer to [Appendix 7](#) for definitions of woman of childbearing potential and adequate contraception):

- Has practiced adequate contraception for 30 days prior to vaccination, and
- Has a negative urine pregnancy test on the day of vaccination, and
- Has agreed to continue adequate contraception during the entire treatment period and for 2 months after completion of the vaccination series.

5.2 Exclusion Criteria

Deviations from exclusion criteria are not allowed because they can potentially jeopardize the scientific integrity, regulatory acceptability of the study, or subject safety. Therefore, adherence to the criteria as specified in the protocol is essential.

The following criteria should be checked at the time of study entry. If ANY exclusion criterion applies, the subject must not be included in the study.

1. Health condition that, in the opinion of the Investigator, may interfere with optimal participation in the study or place the volunteer at increased risk of adverse events (AEs). Study clinicians, in consultation with the Principal Investigator will use clinical judgment on a case-by-case basis to assess safety risks under this criterion. The Principal Investigator will consult with the Medical Monitor as appropriate.
2. Use of any investigational or nonregistered product (drug, vaccine, or medical device) other than the study vaccine(s) during the period starting 30 days before the first dose of study vaccine(s) (Day -29 to Day 1), or planned use during the study period.
3. Any medical condition that in the judgment of the Investigator would make intramuscular (IM) injection unsafe and subjects under treatment with anticoagulant therapy.
4. Chronic administration (defined as more than 14 consecutive days in total) of immunosuppressants or other immune-modifying drugs during the period starting 3 months prior to the first vaccination. For corticosteroids, this will mean prednisone ≥ 5 mg/day (for adult subjects), or equivalent. Inhaled and topical steroids are allowed.
5. Administration of long-acting immune-modifying drugs at any time during the study period (eg, infliximab).
6. Administration of immunosuppressive therapy, including chemotherapeutic agents used to treat cancer or other conditions, and treatments associated with organ or bone marrow transplantation or autoimmune disease.
7. Administration of immunoglobulins and/or any blood products during the period starting 3 months before the first vaccination of study treatment or planned administration during the study period.
8. Planned administration/administration of a vaccine not foreseen by the study protocol in the period starting 6 weeks before the first vaccination and ending 6 weeks after the last vaccination, with the exception of inactivated influenza vaccine which can be administered up to 14 days before or from 30 days after the last study vaccination.
In case an emergency mass vaccination for an unforeseen public health threat (eg, a pandemic) is recommended and/or organized by public health authorities outside the routine immunization program, the time period described above can be reduced if, necessary for that vaccine, provided it is used according to the local governmental recommendations and that the Sponsor is notified accordingly.
9. Planned administration of GSK's Herpes Zoster vaccine marketed as *Shingrix* or an adjuvanted recombinant varicella zoster virus envelope gE subunit vaccine (HZ/su) within 180 days before the first dose and within 180 days after the last dose of the study vaccine.
10. Planned elective surgery during the study period.

11. Concurrently participating in another clinical study, at any time during the study period, in which the subject has been or will be exposed to an investigational or a non-investigational vaccine/product (pharmaceutical product or device).
12. Body mass index $<19 \text{ kg/m}^2$ or $\geq 35 \text{ kg/m}^2$.
13. Clinically relevant physical examination abnormalities.
14. For subjects aged 18–45 years, Grade 2 or higher abnormal hematological, biochemical, and urinary parameters.
15. For subjects aged 50–70 years, Grade 3 or higher abnormal hematological, biochemical, and urinary parameters.
16. Documentation of current or prior episode of CDI.
17. Any confirmed or suspected immunosuppressive or immunodeficient condition, based on medical history and physical examination (no laboratory testing required).
18. Recurrent history or uncontrolled neurological disorders or seizures.
19. Family history of congenital or hereditary immunodeficiency.
20. History of any reaction or hypersensitivity likely to be exacerbated by any component of the vaccines.
21. Acute disease and/or fever at the time of enrollment.
 - Fever is defined as temperature $\geq 38.0^\circ\text{C}/100.4^\circ\text{F}$. The preferred location for measuring temperature in this study will be the oral cavity.
 - Subjects with a minor illness (such as mild diarrhea, mild upper respiratory infection) without fever may, be enrolled at the discretion of the Investigator.
22. Acute or chronic, clinically significant pulmonary, cardiovascular, hepatic, or renal functional abnormality, as determined by physical examination or laboratory screening tests.
23. Pregnant or lactating female.
24. History of intestinal bleeding or history of diverticular intestinal bleeding.
25. Surgery for gastrointestinal malignancy in the period starting 3 months prior to the first vaccination.
26. History of chronic alcohol consumption and/or drug abuse as deemed by the Investigator to render the potential subject unable/unlikely to provide accurate safety reports.
27. Female planning to become pregnant or planning to discontinue contraceptive precautions.
28. Documented human immunodeficiency virus-positive subject, known positivity for the surface Ag of the hepatitis B virus or known positive serologic test for the hepatitis C virus.
29. Involvement in the planning and/or conduct of the study (applies to both GSK personnel and/or personnel at the study center).

5.3 Lifestyle Considerations

No restrictions pertaining to lifestyle and/or diet beyond the details indicated in Section 5.2.

5.4 Screen Failures

Screen failures before first dose are defined as subjects who consent to participate in the clinical study but who are not subsequently randomly assigned to study treatment. Screen failures before third dose are defined as subjects who consent but did not receive the third dose. A minimal set of screen failure information is required to ensure transparent reporting of screen failure subjects to meet the Consolidated Standards of Reporting Trials publishing requirements and to respond to queries from regulatory authorities. Minimal information for screen failures before first dose includes demography, screen failure details, eligibility criteria, and any serious adverse events (SAEs). Minimal information for screen failures before third dose includes screen failure details, eligibility criteria, and any SAEs.

Upon completion of all screening procedures (refer to Section 1.3), the Investigator will review the inclusion/exclusion criteria for each subject. Subjects meeting all eligibility criteria will be enrolled in the study. Their screening information will be recorded in the eCRF.

If the Investigator believes there is a reasonable justification to do so, screening procedures may be repeated (maximum 1 Rescreening per subject is allowed).

Only laboratory results from the Rescreening Visit, if it occurs, will be taken into consideration and recorded in the eCRF. Medical history, physical examination and review of inclusion/exclusion criteria must be repeated if a Rescreening Visit occurs. The subject can only be randomized once the Investigator receives the results and confirms the eligibility criteria.

6.0 STUDY TREATMENT

Study treatment is defined as a set of investigational product(s) or marketed product(s) or placebo intended to be administered to a subject.

6.1 Study Treatment(s) Administered

Table 14 Description of Study Treatment

Treatment Name	Vaccine Name	Formulation	Presentation	Volume to be Administered	Number of Doses
Placebo	NaCl	NaCl = 150mM	Clear liquid for suspension	0.5 mL	2 doses
CDIFF Ag	F2	F2 antigen	Lyophilized	0.5 mL	2 or 3 doses*
	NaCl	NaCl = 150mM	Clear liquid for suspension		
CDIFF Ag + AS01 _B	F2	F2 antigen	Lyophilized	0.5 mL	2 or 3 doses*
	AS01 _B	MPL = 50 µg; QS-21 = 50 µg; Liposomes	Liquid in a monodose vial		

Ag = antigen; AS01_B = an adjuvant system containing MPL, QS-21 and liposome (50 µg MPL and 50 µg QS-21);

GSK = GlaxoSmithKline Biologicals SA; MPL = 3-O-desacyl-4'-monophosphoryl lipid A; QS-21 = *Quillaja saponaria* Molina, fraction 21 (Licensed by GSK from Antigenics Inc., a wholly owned subsidiary of Agenus Inc., a Delaware, USA corporation)

* *a third dose will be administered to a subcohort of subjects in Step 4*

Table 15 Dosage and Administration of Study Treatment

Type of Contact and Timepoint	Study Group	Treatment Name	Volume to be Administered	Route	Injection Site	
					Location	Laterality ^a
Visit 1 (Day 1)	Placebo	Placebo	0.5 mL	IM	Deltoid	Nondominant
	CDIFF Ag	CDIFF Ag	0.5 mL	IM	Deltoid	Nondominant
	CDIFF Ag + AS01 _B	CDIFF Ag + AS01 _B	0.5 mL	IM	Deltoid	Nondominant
Visit 3 (Day 31)	Placebo	Placebo	0.5 mL	IM	Deltoid	Nondominant
	CDIFF Ag	CDIFF Ag	0.5 mL	IM	Deltoid	Nondominant
	CDIFF Ag + AS01 _B	CDIFF Ag + AS01 _B	0.5 mL	IM	Deltoid	Nondominant
Visit 8 (Day 491)	CDIFF Ag	CDIFF Ag	0.5 mL	IM	Deltoid	Nondominant
	CDIFF Ag + AS01 _B	CDIFF Ag + AS01 _B	0.5 mL	IM	Deltoid	Nondominant

Ag = antigen; AS01_B = an adjuvant system containing MPL, QS-21 and liposome (50 µg MPL and 50 µg QS-21);

IM = intramuscular; MPL = 3-O-desacyl-4'-monophosphoryl lipid A.

^a The nondominant arm is the preferred arm of injection. In case it is not possible to administer the vaccine in the nondominant arm, an injection in the dominant arm may be performed.

For each subject, the Investigator is not permitted to start the administration of the next dose until receipt of the favorable outcome of the safety evaluation, documented and provided in writing (scanned and emailed), authorizing the Investigator to proceed. Moreover, if the Investigator becomes aware of a holding rule being met, he/she will suspend vaccination and will inform GSK immediately (see [Table 11](#) and [Table 12](#)).

Refer to Section [4.6.1](#) for detailed description of holding rules and safety monitoring.

The subjects will be observed closely for at least 60 minutes following the administration of the vaccine(s), with appropriate medical treatment readily available in case of anaphylaxis and syncope.

6.2 Contraindication to Subsequent Vaccination

Prior to receipt of additional study vaccination, subjects must be evaluated to confirm that they are eligible for subsequent vaccination.

If subjects meet any of the original exclusion criteria or the criteria listed below, they should not receive additional vaccinations. However, the subjects should be encouraged to continue other study procedures at the discretion of the Investigator (Section [8.3.3](#)).

- Subjects who experience any SAE judged to be possibly or probably related to study vaccine or non-study vaccines, including hypersensitivity reactions.

- Subjects who develop any new condition which, in the opinion of the Investigator, may pose additional risk to the subject if he/she continues to participate in the study.
- Anaphylaxis following the administration of vaccines.
- Grade 3 or higher abnormal hematological, biochemical, and urinary parameters.
- Occurrence of a new potential immune-mediated disease (pIMD) or the exacerbation of an existing pIMD that, in the opinion of the Investigator, expose the subject to unacceptable risk from subsequent vaccination. In such cases, the Investigator should use his/her clinical judgment prior to administering the next dose of the vaccine(s)/product(s). Refer to [Appendix 2](#) for the definition of pIMDs.

6.3 Criteria for Temporary Delay of Vaccination

Vaccination may be postponed within the allowed time interval until transient circumstances cited below have been resolved.

Acute disease and/or fever at the time of vaccination.

- Fever is defined as temperature $\geq 38.0^{\circ}\text{C}/100.4^{\circ}\text{F}$. The preferred location for measuring temperature in this study will be the oral cavity.
- Subjects with a minor illness (such as mild diarrhea, mild upper respiratory infection) without fever can be administered all vaccines.

6.4 Intercurrent Medical Condition That May Lead to Elimination of a Subject From the Per-protocol Analysis

At each study visit subsequent to the first vaccination/the vaccination visit, it must be verified if the subject has experienced or is experiencing any intercurrent medical condition that may lead to elimination from the per-protocol analysis. If it is the case, the condition(s) must be recorded in the eCRF.

Subjects may be eliminated from the Per-protocol Set for analysis of immunogenicity if, during the study, they incur a condition that has the capability of altering their immune response or are confirmed to have an alteration of their initial immune status.

6.5 Preparation/Handling/Storage/Accountability

The study vaccine(s) must be stored at the respective label storage temperature conditions in a safe and locked place. Access to the storage space should be limited to authorized study personnel. The storage conditions will be assessed during prestudy activities under the responsibility of the Sponsor study contact. The storage temperature should be continuously monitored with calibrated (if not validated) temperature monitoring device(s) and recorded. Refer to the Module on Clinical Trial Supplies in the Study Procedures Manual (SPM) for more details on storage of the study vaccine(s).

A temperature excursion is any temperature that is not in range of the label storage temperature conditions. Temperatures outside the range of label storage temperature conditions must be reported and/or documented. Temperature excursion impacting study vaccine(s) must be reported and/or documented.

In the frame of the reporting, the lack/absence of temperature monitoring documentation from a device meeting GSK requirements has to be considered as a temperature excursion.

Study vaccine(s) that are impacted by a temperature excursion may not be used and must be quarantined at label storage conditions until usage approval has been obtained from/via the local study contact (eg, study center monitor).

Refer to the Module on Clinical Trial Supplies in the SPM for details and instructions on the temperature excursion reporting and usage decision process, packaging and accountability of the study vaccine(s).

6.5.1 Replacement of Unusable Vaccinations

In addition to the vaccine doses provided for the planned number of subjects (including over-randomization when applicable), at least 20% additional vaccine doses will be supplied to replace those that are unusable.

The Investigator will use a System Built for Internet Randomization (SBIR) to obtain the replacement dose number. The replacement numbers will be allocated by component. The system will ensure, in a blind manner, that the replacement dose matches the formulation the subject was assigned to by randomization.

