6.6.2.1 Treatment Number Allocation for Subsequent Doses

For each dose subsequent to the first dose, the study staff in charge of the vaccine administration will access SBIR, provide the subject identification number, and the system will provide a treatment number consistent with the allocated study group.

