6.6.3 Blinding

Data will be collected in an observer-blind manner. By observer-blind, it is meant that during the course of the study, the vaccine recipient and those responsible for the evaluation of any study endpoint (eg, safety and reactogenicity) will all be unaware of which vaccine was administered. To do so, vaccine preparation and administration will be done by authorized medical personnel who will not participate in any of the study clinical evaluations. The Investigator and the subjects will not have access to the treatment allocation up to Day 390.

The statistical analyses will be performed in 3 steps. Refer to Section 9.8 for controlled unblinding for the first and second interim analysis.

The data for third dose will be collected in a partial blind manner.

After Day 390, only the subjects will remain fully blinded. Those responsible for the evaluation of any study endpoint (eg, safety and reactogenicity) will be partially blinded, as no placebo subjects will be included for Dose 3.

The laboratory in charge of the laboratory testing will be blinded to the treatment, and codes will be used to link the subject and study (without any link to the treatment attributed to the subject) to each sample.

6.6.3.1 *Emergency Unblinding*

Unblinding of a subject's individual treatment code should occur only in the case of a medical emergency when knowledge of the treatment is essential for the clinical management or welfare of the subject.

The emergency unblinding process consists of the automated internet-based system (SBIR) that allows the Investigator to have unrestricted, immediate and direct access to the subject's individual study treatment.

As back-up process, the Investigator has the option of contacting a GSK Helpdesk (refer to [Table 16](#)) if he/she needs support to perform the unblinding (ie, he/she cannot access SBIR).

Non-investigator physician (eg, physician from emergency room) or subject/care giver/family member can also request emergency unblinding either via the Investigator (preferred option) or via the GSK Helpdesk (back-up process). Contact details of Investigator and GSK Helpdesk are reported in the subject card.

Table 16 Contact Information for Emergency Unblinding

GSK Helpdesk
24-hour and 7-day availability
The Helpdesk is available by phone, fax and email
Toll-free number: [name]
[contact]
[contact]
email: [contact]

A subject may continue in the study if that subject's treatment assignment is unblinded.

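### Protocol 6.5.1 has the blinded Investigator obtain replacement doses by component, contrary to the role separation in 6.6.2 to 6.6.3, which opens a possible route to unblinding

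*Protocol*

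**What the plan says.** **Replacement doses.** Protocol 6.5.1 names both the user and the unit: "The Investigator will use a System Built for Internet Randomization (SBIR) to obtain the replacement dose number. The replacement numbers will be allocated by component". It then adds a safeguard: "The system will ensure, in a blind manner, that the replacement dose matches the formulation the subject was assigned to by randomization".

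**Ordinary doses.** Under 6.6.2, treatment numbers are allocated by dose, and the staff in charge of giving the vaccine use SBIR for the first dose. For later doses 6.6.2.1 says the same: "the study staff in charge of the vaccine administration will access SBIR, provide the subject identification number". SAP 3.4 repeats the first-dose rule and does not mention replacements.

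**Blinding.** Protocol 4.2.1 explains that the products look different, so the study is observer-blind. Section 6.6.3 achieves this by separating roles: "vaccine preparation and administration will be done by authorized medical personnel who will not participate in any of the study clinical evaluations". The same section keeps allocation from the Investigator up to Day 390. After that, assessors are called partially blinded because no placebo subject receives Dose 3.

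**Components.** In Table 14 (6.1), placebo is NaCl alone ("Clear liquid for suspension"). CDIFF Ag is lyophilized F2 with NaCl. CDIFF Ag + AS01B is lyophilized F2 with a separate AS01B presentation ("Liquid in a monodose vial").

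**Assessment.** Appendix 6 has the Investigator grade the intensity of unsolicited AEs and judge causality for every AE except solicited local reactions, which count as related by rule.

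**The concern.** Because the products cannot be made to look alike, the blind depends on keeping the people who handle product apart from the people who assess subjects. Section 6.5.1 crosses that line: it gives a product-related SBIR task to the assessor, in units that differ between arms. Ordinary doses do not have this feature, since their numbers are allocated by dose and drawn by other staff.

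The primary endpoints at stake are those that rest on the Investigator's judgement: relatedness of solicited general symptoms, and intensity and relatedness of unsolicited AEs. An assessor who knows or suspects the arm may judge these differently. Dose 3 has no placebo group, so which active formulation a subject receives is all that remains to be protected from the Investigator.

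**Working it through.** The plan gives no figure to reproduce. The check sets components against arms and asks what a requester would learn on knowing which component was replaced.

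**Inputs.** Components come from Table 14, as above. Planned group sizes come from Table 10:

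- Steps 1 and 2: placebo 10, CDIFF Ag 10 (each step).
- Step 3: placebo 10, CDIFF Ag 10, CDIFF Ag + AS01B 10.
- Step 4: placebo 10, CDIFF Ag 25, CDIFF Ag + AS01B 35.
- Step 4, Dose 3: CDIFF Ag 25, CDIFF Ag + AS01B 35, if all active subjects continue.

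**Formula.** Within a step, P(arm | component) = n(arm) / sum of n over the arms that use the component. This assumes a component is equally likely to be unusable in every arm that uses it.

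| Setting | Component | Calculation | What it would reveal |
|---|---|---|---|
| Steps 1-2 | F2 | 10/10 | CDIFF Ag, 100% |
| Steps 1-2 | NaCl | 10/20 each | nothing: 50/50, as before the request |
| Step 3 | AS01B | 10/10 | adjuvanted arm, 100% |
| Step 3 | F2 | 10/20 each | placebo excluded; 50/50 between active arms |
| Step 3 | NaCl | 10/20 each | adjuvanted arm excluded; 50/50 placebo or CDIFF Ag |
| Step 4, Doses 1-2 | AS01B | 35/35 | adjuvanted arm, 100% |
| Step 4, Doses 1-2 | F2 | 35/60 and 25/60 | placebo excluded; 58.3% adjuvanted, 41.7% CDIFF Ag |
| Step 4, Doses 1-2 | NaCl | 25/35 and 10/35 | adjuvanted arm excluded; 71.4% CDIFF Ag, 28.6% placebo |
| Step 4, Dose 3 | NaCl | 25/25 | CDIFF Ag, 100% |
| Step 4, Dose 3 | AS01B | 35/35 | adjuvanted arm, 100% |
| Step 4, Dose 3 | F2 | 35/60 and 25/60 | nothing: same as before the request |

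The 100% rows follow from Table 14 and the arms open in that setting. They do not need the equal-likelihood assumption; the other percentages do.

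Some narrowing is slight. In Step 4 at Doses 1-2 the chance of being on an active arm is already 60/70 = 85.7%, and an F2 request raises it to 100%.

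**Weight of one subject.** SAP 6.2 generally presents data by age group and treatment, pooled over steps. One subject aged 50-70 is 1/45 = 2.2% of an active group or 1/30 = 3.3% of placebo. One subject aged 18-45 is 1/10 = 10% of a group.

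**The case against.** **The safeguard sentence.** Section 6.5.1 says the matching is done blind, and nothing describes the replacement screen. The SPM and the SBIR user guide, which 6.5 and 6.6.2 cite for supply and system details, are not available here. A reader might infer that 6.5.1 breaks the observer blind; the documents do not support that. The sentence covers the match between replacement and assigned formulation. It says neither that the component is hidden from the user nor that it is shown. The route stays open, but unblinding is not established.

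**Delegation.** Appendix 2 lets the Investigator delegate duties, and 6.6.3 leaves preparation to separate staff, who would normally be the ones to find an unusable vial. In practice those staff may make the request. That is plausible, but delegation is permitted, not required. A blinded Investigator who makes the request personally would be following 6.5.1 as written.

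**SBIR access is not itself a breach.** Section 6.6.3.1 already gives the Investigator SBIR access for emergency unblinding. That stands, but it is reserved for medical emergencies, whereas replacement is routine supply work.

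**Limited exposure.** Solicited symptoms are recorded on subjects' diary cards, and solicited local reactions are related by rule. This stands too: only judgement-based causality and unsolicited intensity are open to influence.

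**Conclusion.** The conflict of roles is real and can be read directly from the text: 6.5.1 names a blinded assessor for a task that 6.6.2, 6.6.2.1 and 6.6.3 would leave with staff outside clinical evaluation. The consequence is potential and unquantified. It requires that the Investigator makes the request personally and that the component is visible when doing so; the documents settle neither.

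If both hold, some requests identify the arm, some narrow it and some reveal nothing, as tabulated. It would be wrong to treat every component request as informative.

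Two figures might tempt a reader to a larger claim. Section 6.5.1 supplies at least 20% extra doses, about 68 on 340 planned doses (140 x 2 + about 60 = 340; 340 x 0.20 = 68). That is a supply minimum, not an expected number of replacements. And one subject is 10% of a step-level group of 10, but the main summaries pool over steps, so 10% applies only to the two groups aged 18-45. No estimate of bias can be given.

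**What to change.** In 6.5.1, replace the Investigator as SBIR user with *the study staff in charge of vaccine preparation and administration, who take no part in clinical evaluations*. Add that the identity of the replaced component is not shown to blinded personnel until unblinding.

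The replacement number should not be kept out of the eCRF, because 6.6.2 requires each administered treatment number to be recorded there. It should be recorded in a form that does not reveal the component.

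The cost is protocol wording, matching SPM text and an SBIR user-role setting. The vaccine-administration staff already use SBIR for every dose, so no extra staff are needed.
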